6.6 Missing Data

All efforts will be made to collect all data points in this study. Missing data will be imputed for the primary endpoint by assuming the missing outcomes represent no change from baseline. Additional post hoc sensitivity analyses may be performed if missing cases exceed 10% of the sample size, including a worst-case analysis (all missing rTNSS at 3 months are the worst possible score), to further assess the effect of missing data on the primary analysis. The results of the sensitivity analysis will not be used to adjust the conclusions drawn from the primary analysis.

Secondary outcome measures and additional observational measurements will be analyzed by using available data only.

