6.3 Sample Size Estimate

The study will enroll up to 140 participants. The power analysis was performed such that there is adequate power to reject the null hypothesis that the mean improvement from baseline in rTNSS is 1 point or less. Sample size estimation was based on a paired t-test for change from baseline at 13 weeks using the following assumptions:

- Significance level $\alpha = 0.025$ (one-sided)
- Power = 90%
- $\mu_d = 1$ -point decrease in mean change score = MCID
- SD = 3 = estimated standard deviation of the mean difference based on an observed SD of 2.6 in a prior study.

RhinAer RELIEF single arm protocol Rev C Final 27JAN2021CONFIDENTIAL

The minimum number of subjects to achieve 90% power is 97 (G-Power, paired ttest). Allowing for 15% loss (nonevaluable) and adjusting for a balanced distribution across 20 sites the sample size is 140 participants. It is anticipated that participants will be enrolled at sites on a competitive basis; however, a reasonable balance of participants among sites may be maintained by potentially capping enrollment at individual sites based on the final number of participating sites.

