6.5 Analysis Populations

Enrolled Population – all subjects enrolled in the study.

Evaluable Population – all subjects that are enrolled in the study and have received the study procedure.

Safety Population – all subjects enrolled in the study.

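### The power in section 6.3 ignores the zero-change imputation in section 6.6: at the plan's own 15% loss it could be about 82% rather than 95%, if a 2-point decrease is the intended alternative

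*Combined protocol and SAP*

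**What the plan says.** Four parts of the combined protocol and SAP bear on this.

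- **Section 6.3, Sample Size Estimate.** The aim is to "reject the null hypothesis that the mean improvement from baseline in rTNSS is 1 point or less". The inputs are one-sided alpha 0.025, power 90%, an effect given as a 1-"point decrease in mean change score = MCID", and SD 3, described as the "estimated standard deviation of the mean difference based on an observed SD of 2.6 in a prior study". The result is: "The minimum number of subjects to achieve 90% power is 97". Then: "Allowing for 15% loss (nonevaluable) and adjusting for a balanced distribution across 20 sites the sample size is 140 participants".
- **Section 6.5, Analysis Populations.** The Evaluable Population is "all subjects that are enrolled in the study and have received the study procedure". A 3-month score is not required.
- **Section 6.6, Missing Data.** "Missing data will be imputed for the primary endpoint by assuming the missing outcomes represent no change from baseline". Further sensitivity analyses may be run if more than 10% of cases are missing.
- **Section 6.10, Primary Endpoint Analysis.** A one-sided paired t-test of the mean change against the 1-point MCID. No analysis population is named.

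**The concern.** The loss allowance in section 6.3 describes people who drop out of the calculation: enrol more, lose some, and test those who remain. Section 6.6 describes something else. A treated participant with no 3-month score stays in the test with a change of zero.

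Against a null of no change, that would only dilute the effect. Here the null boundary is a 1-point decrease, so a zero lies on the null side of it. Imputation shrinks the distance between the mean and the boundary faster than it shrinks the mean itself, and it adds variance between the imputed and observed groups. Dividing n by (1 − 0.15) corrects for neither.

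At stake is whether the 90% in section 6.3 describes the analysis that will be run, and whether 15% loss is compatible with it.

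**Working it through.** **Inputs.** From section 6.3: one-sided alpha 0.025, SD 3 (2.6 observed in a prior study), 97 for 90% power, 15% loss, 140 enrolled. From section 6.2: null boundary at a 1-point decrease. From section 1.0: a 5.1-point improvement in the earlier 50-participant study. **Assumption:** a true mean decrease of 2 points among those observed.

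**Step 1: reproduce 97.** For a paired t-test the noncentrality is (δ − 1)/SD × √n, where δ is the true decrease. With δ = 2, SD = 3 and n = 97 it is (1/3) × √97 = 3.283, and the noncentral t gives power 90.1%. At n = 96 it is 89.8%. So 97 is reproduced, and against the stated null with SD 3 it requires a distance of 1 point beyond the boundary, that is, δ = 2.

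**Step 2: loss as section 6.3 treats it.** 15% of 140 is 21, leaving 119. The noncentrality is (1/3) × √119 = 3.636 and power is 95.0%. This is the like-for-like comparator. The 90% belongs to 97 analysed participants.

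**Step 3: loss as section 6.6 treats it.** Let a share m of those analysed have change 0 and the rest have mean decrease δ.

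- Mean decrease = (1 − m)δ = 0.85 × 2 = 1.70, which is 0.70 beyond the boundary.
- Variance = (1 − m)SD² + m(1 − m)δ² = 0.85 × 9 + 0.15 × 0.85 × 4 = 7.65 + 0.51 = 8.16, so SD = 2.857.
- Noncentrality = 0.70/2.857 × √140 = 2.899, and power is 82.1%.

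Simulation of 200,000 trials gives 82.5% with random loss and 83.3% with exactly 21 lost.

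**Step 4: how far the answer moves.** Same method. Unless stated, 140 analysed, SD 3, δ = 2, 15% imputed.

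| Change to the inputs | Power |
|---|---|
| 5% imputed | 94.7% |
| 9% imputed | 91.0% |
| 10% imputed | 89.8% |
| 20% imputed | 71.2% |
| 7 of the 21 lost are untreated and excluded (133 analysed, 14 imputed) | 87.6% |
| 14 of the 21 lost are untreated and excluded (126 analysed, 7 imputed) | 91.8% |
| SD 2.6 | 90.8% |
| δ = 2.5 | 99.5% |
| δ = 5.1 | about 100% |

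At 140, power reaches 90% when at most about 9.9% are imputed, or, with 15% imputed, when δ is about 2.11 or more.

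**Step 5: other readings of the effect.** A true decrease of 1 against a null of 0 also gives 97, and yields 94.8% with 15% imputed at 140, but that null contradicts sections 6.2, 6.3 and 6.10. Read literally, a true decrease of 1 against a boundary of 1 gives 2.5% with no loss and 0.5% with 15% imputed, which cannot be intended.

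**The case against.** A reader might infer that the trial has 82% power instead of 90%. The documents do not support that as an unconditional statement, for four reasons.

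- **The 2-point alternative is inferred.** Section 6.3 states only a 1-point effect. This stands as a limit on the figure. Even so, 2 points is not arbitrary: it is what makes the plan's own 97 correct against its own null.
- **The 15% may not all be imputed.** Section 6.3 calls the loss nonevaluable, and section 6.5 makes evaluability depend on treatment alone. Under section 5.4 a participant is enrolled on eligibility and consent, before treatment, and section 6.8 foresees an enrolled-but-untreated group. If the primary test uses the Evaluable Population, untreated participants leave it, as section 6.3 assumes. If all 21 were untreated, power would be 95.0%. Section 6.10 names no population, so the documents cannot settle the split.
- **SD 3 is deliberately above the observed 2.6.** At 2.6 power stays just above 90%. This stands, although the imputation still costs about 8 points there (98.6% with the lost removed, 90.8% with them imputed).
- **The practical risk is small.** The earlier study's 5.1-point effect gives power near 100%. Scoring missing outcomes as no change also works against study success, so it does not raise the false-positive risk.

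It would also be too strong to say that the plan gives no thought to the amount of missing data. The 10% trigger in section 6.6 lies close to the 9.9% break-even. But that trigger is not linked to power, and section 6.3 plans for 15%.

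**Conclusion.** The mismatch between sections 6.3 and 6.6 is real: the power calculation makes no allowance for outcomes imputed as zero change. With a true 2-point decrease, SD 3, and all of the 15% treated but missing the 3-month score, the cost at 140 is about 13 percentage points, from 95% to 82%. Under other inputs that the documents leave open, power stays above 90%.

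The shortfall is therefore conditional, and confidence in its size is moderate. The documents do not support the conclusion that the trial is too small. They do support the narrower one: the stated 90% cannot be taken as the power of the planned primary analysis at the plan's own loss rate until the true change and the analysis population are stated.

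**What to change.** Three short edits:

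1. In section 6.3, state the assumed true mean change separately from the 1-point null boundary.
2. In section 6.10, name the primary analysis population, so that it is clear whether enrolled but untreated participants are excluded or imputed.
3. In section 6.3, restate power under the section 6.6 rule. If 2 points is the intended alternative, for example: *With 140 treated and 15% imputed as no change, power is about 82% for a true 2-point decrease (SD 3); at least 90% holds with about 9% or less missing.*

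The last clause can also serve as the retention target for the 3-month visit.

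No additional enrolment is needed, and the test and the imputation rule are unchanged. The cost is a less favourable power figure in the protocol.

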6.7 Pooling

All study data will be pooled across study sites to facilitate hypothesis testing in accordance with the sample size estimation and power analysis (Section 6.3). Pooling is generally justified because the study will be conducted such that: 1) the same protocol will be used at each site; 2) site investigators and personnel will receive uniform training; and 3) central data management and monitoring will be consistent and applied with equal rigor at all sites. Comparability between study sites may be shown using summary statistics calculated by site.

RhinAer RELIEF single arm protocol Rev C Final 27JAN2021CONFIDENTIAL

6.8 Participant Disposition

A detailed description of participant disposition will be provided using a CONSORT diagram and summaries of participants falling in various subgroups of interest, such as, enrolled but not treated, discontinued, protocol deviations, deaths, and withdrawals. All study population exclusions and reasons will be summarized. Follow-up by visit will be presented, showing theoretical, expected, and actual follow-up visits.

6.9 Demographics and Baseline Characteristics

Demography and other baseline characteristics will be summarized using frequencies and percentages for categorical factors and mean, median, standard deviation, minimum and maximum for continuous factors. Demographic characteristics will be reported to describe the profile of samples.

Baseline covariates with possible impact on outcomes at 3 months are:

- Age
- Race
- Sex
- BMI
- Allergic status (allergic rhinitis nonallergic rhinitis).

Results may be evaluated by allergic status if sufficient numbers are obtained in both categories.

6.10 Primary Endpoint Analysis

The mean change in the rTNSS from baseline to 13 weeks will be tested using a paired t-test for a significant decrease greater than the MCID under the one-sided null and alternative hypotheses.

A *P* value for the test statistic \leq .025 will indicate that the mean decrease is statistically significantly greater than 1 point. The upper limit of the one-sided 97.5% confidence interval on the mean decrease will also be calculated.

6.11 Secondary Endpoints Analysis

Secondary endpoints will be formally tested only after the primary objective of the study is met. Confidence intervals (95%) will be included for all secondary outcome measures.

• Responder percentage at 13 weeks

The proportion of responders will be calculated along with the 95% confidence interval. Individual participant success (responder) is defined as at least 30% improvement (decrease) in the 24-hour reflective Total Nasal Symptom Score (rTNSS). An overall responder percent of at least 60% is

expected for the study. The observed proportion of responders will be compared to the expected proportion with a binomial test.

• Mean change in the Mini Rhinoconjunctivitis Quality of Life Questionnaire (MiniRQLQ) score from baseline to 13 weeks after the study procedure.

The mean change in the MiniRQLQ score from baseline to 13 weeks will be tested using a paired t-test for a significant decrease greater than the MCID.

• Device-related and procedure-related serious adverse events through 13 weeks

The proportions of serious device-related adverse events through 13 weeks will be calculated along with the 95% confidence interval.

6.12 Other Outcome Measures Analyses

Additional outcome measures will be collected for information and hypothesis generating purposes. The primary analysis methods will be descriptive and exploratory and presented by evaluation to more completely understand the time course of treatment effect. Measures will be summarized using frequencies and percentages for categorical measures and mean, median, standard deviation, minimum and maximum for continuous factors. Confidence intervals will be included where appropriate. Statistical comparisons will either not be performed or used for information purposes. Proportions may be compared using t-tests, ANOVA or nonparametric equivalents. Repeated measures ANOVA or mixed effects modeling may be used for longitudinal analysis across evaluations.

Other outcome measures include:

- Nasal Assessment The visual physical and endoscopic assessment factors will be summarized to include frequency and percentage of responses in each category for each component of the nasal assessment at baseline, just prior to treatment, immediately after treatment, and at 3 months after the procedure.
- Visual analog scale (VAS) for pain Summary will include mean VAS pain scores assessed posttreatment and at 3 months.
- rTNSS The rTNSS and its individual components will be subject to multiple summary methods and analyses including the:
 - Mean and mean change from baseline at the 3-, 6-, 12-, 24-, and 36month follow-up evaluations.
 - Mean, mean change from baseline, and response distribution of the 4 components of the rTNSS (rhinorrhea, nasal congestion, nasal itching, and sneezing) at baseline and the 3-, 6-, 12-, 24-, and 36-month follow-up evaluations.

RhinAer RELIEF single arm protocol Rev C Final 27JAN2021CONFIDENTIAL

- Proportion of responders based on 30% improvement in rTNSS at the 3-, 6-, 12-, 24-, and 36-month follow-up evaluations.
- Other rhinitis symptoms (cough and postnasal drip) Mean, mean change from baseline, and distribution of the 4 response categories (0-3 points) at baseline and the 3-, 6-, 12-, 24-, and 36-month follow-up evaluations.
- MiniRQLQ: The MiniRQLQ and its individual components will be subject to multiple summary methods and analyses including the:
 - MiniRQLQ mean and mean change from baseline at the 3-, 6-, 12-, 24-, and 36-month follow-up evaluations.
 - MiniRQLQ domain scores (nose symptoms, eye symptoms, noneye/nose symptoms, sleep problems, practical problems, activity limitations, and emotional function) at baseline and the 3-, 6-, 12-, 24-, and 36-month follow-up evaluations.
- Participant satisfaction assessment mean response for each of the 5 survey questions will be summarized at the 3-, 6-, 12-, 24-, and 36-month follow-up evaluations.
- Change in amount of PRN medication use for chronic rhinitis symptoms -Proportions of participants reporting increase, decrease, or no change in medications being used for treatment of symptoms compared to use prior to the procedure will be summarized for the 3-, 6-, 12-, 24-, and 36-month follow-up evaluations.
- Medications A listing of medications associated with relief or treatment of chronic rhinitis symptoms or associated with treatment of adverse events will be provided. Medication use by categories may also be presented as percentages of participants.

6.13 Safety Analysis

All adverse events will be analyzed for all participants. Adverse events will be coded using a custom Aerin Medical dictionary so that adverse events may be categorized for analysis at an appropriate level of detail. Listings will be provided to detail individual events. The number of participants, number of AEs, and the proportion of participants reporting each AE will be summarized. Seriousness and severity of AEs and their relationship to the device and procedure will be summarized. A time course of adverse events will be presented. Any unexpected adverse device experiences or adverse events that occur at an unexpectedly high incidence rate will receive detailed analyses. Narratives will be presented for all deaths, serious adverse events, unexpected adverse device experiences, and participants withdrawn due to an adverse event.

6.14 Extension Phase Analysis

The extension phase analyses will be similar to those detailed above with a particular emphasis on the summarization of all adverse events occurring throughout the entire

RhinAer RELIEF single arm protocol Rev C Final 27JAN2021CONFIDENTIAL

study and the maintenance of the treatment effect over time. Missing data analyses and imputation will not be performed on data collected during the extension phase.

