
RhinAer RELIEF single arm protocol Rev C Final 27JAN2021CONFIDENTIAL

All participants will be evaluated prior to treatment and following treatment at week 13 (3 months). The 3-month evaluation will be used for the primary endpoint analysis.

The study will have an extended follow-up phase with evaluations conducted at 26 weeks (6 months), 52 weeks (12 months), 104 weeks (24 months) and 156 weeks (36 months) to provide additional information on longer-term efficacy and duration of treatment effect.

StudyThe primary objective is to assess the performance of the RhinAerObjective:procedure with respect to mean change in the 24-hour reflective Total
Nasal Symptom Score (rTNSS) at 3 months posttreatment when used as
a treatment for chronic rhinitis. A secondary objective is the evaluation
of treatment effect duration through an extended follow-up to 36 months.

PrimaryMean change in the 24-hour rTNSS from baseline to 3 months after the**Endpoint:**study procedure.

- Participant responder percentage, defined as the proportion of participants achieving a successful outcome at the 3-month evaluation. A successful outcome is defined as a 30% improvement (decrease) in the rTNSS.
 - Mean change in the Mini Rhinoconjunctivitis Quality of Life Questionnaire (MiniRQLQ) score from baseline to 3 months after the study procedure.
 - Frequency of device-related and procedure-related serious adverse events through the 3-month evaluation.

OtherAdverse events - Incidence (type and category) of adverse events overallOutcomeand by follow-up interval.

Measures: Nasal Assessment – The target posterior nasal nerve area within each nostril will be visually assessed at baseline, following the treatment procedure and at 3 months. The use of an endoscope for visual assessment is required. Representative still photographs or video of each nostril will be captured for each assessment.

Visual analog scale (VAS) for pain - perception of pain associated with the procedure on a 0 to 100 mm scale (0 indicating no pain and 100 indicating the worst pain ever) assessed posttreatment and at 3 months.

rTNSS:

- rTNSS mean and change from baseline at the 3-, 6-, 12-, 24- and 36-month follow-up evaluations.
- rTNSS Individual Nasal Symptom Scores (rhinorrhea, nasal congestion, nasal itching, and sneezing) at baseline and at the 3-, 6-, 12-, 24-month and 36-month follow-up evaluations.

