3.2 Secondary Objectives

Additional objectives include assessment and comparison of secondary endpoints and informational outcome measures.

Secondary endpoints are:

- Participant responder percentage at 3 months. Individual participant success (responder) is defined as at least 30% improvement (decrease) in the 24-hour reflective Total Nasal Symptom Score (rTNSS).
- Mean change in the Mini Rhinoconjunctivitis Quality of Life Questionnaire (MiniRQLQ) score from baseline to 3 months after the study procedure.
- Frequency of device-related and procedure-related serious adverse events through the 3-month evaluation.

Informational outcomes include:

- Adverse events Incidence (type and category) of adverse events overall and by follow-up interval.
- Nasal Assessment The target PNN area within each nostril will be visually assessed at baseline and following the treatment procedure at all evaluations. The use of an endoscope for visual assessment is required. Representative still photographs or video of each nostril will be captured at each visit.

RhinAer RELIEF single arm protocol Rev C Final 27JAN2021CONFIDENTIAL

- Visual analog scale (VAS) for pain perception of pain associated with the procedure on a 0 to 100 mm scale with 0 indicating no pain and 100 indicating the worst pain ever posttreatment through 3 months.
- rTNSS:
 - rTNSS mean and change from baseline at the 3-, 6-, 12-, 24-, and 36month follow-up evaluations.
 - rTNSS Individual Nasal Symptom Scores (rhinorrhea, nasal congestion, nasal itching, and sneezing) at baseline and the 3-, 6-, 12-, 24-, and 36-month follow-up evaluations.
 - Proportion of responders based on improvement in rTNSS at the 3-, 6-, 12-, 24-, and 36-month follow-up evaluations.
- MiniRQLQ:
 - MiniRQLQ mean and change from baseline at the 3-, 6-, 12-, 24-, and 36-month follow-up evaluation.
 - MiniRQLQ domain scores (activity limitations, practical problems, nose symptoms, eye symptoms, and other symptoms) at baseline and the 3-, 6-, 12-, 24-, and 36-month follow-up evaluations.
- Participant satisfaction assessment Five-question self-reported survey of satisfaction with the procedure and recommendation to others summarized by question at the 3-, 6-, 12-, 24-, and 36-month follow-up evaluations.

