4.9 Risk/Benefit Analysis

4.9.1 Risks

Potential risks associated with the use of the RhinAer Stylus do not differ from commonly used devices and treatments for chronic rhinitis, but due to the nonsurgical nature of the therapy, small treatment area, low energy delivery, and lack of need for general anesthesia, the overall risk to the participant may be less than presented by other surgical treatments.

Potential risks associated with the use of the RhinAer Stylus and the associated local anesthetics are listed below. Participants will be monitored closely as part of this study to allow for early detection of potential problems and prompt treatment if required.

Adverse events or side effects that may occur as a result of the treatment include:

- External deformity
- Blanching (generalized whiteness)
- Bruising including around the orbital area (black eyes)
- Infection
- Bleeding (other than during the treatment at treatment sites and greater than anticipated by the investigator)
- Mucosal changes
- Scar formation leading to nasal obstruction
- Sensory changes at treatment site
- Dry eye
- Vasovagal response secondary to the procedure

Anticipated observations that are expected in and around the treatment area and are considered minor include:

- Inflammation / generalized redness
- Temporary swelling, edema
- Temporary numbness/tingling
- Temporary soreness/pain
- Mild bleeding at anesthetic injection and/or treatment site (not requiring physician-level intervention, such as cautery)
- Temporary nasal obstruction from tissue edema
- Disruption of mucosal flow/intranasal crusting
- Scab formation.

These observations will be assessed in the nasal assessment and recorded at study visits if they occur. Should any of the following require mitigation by the treating physician or be greater in severity or degree of incidence than

RhinAer RELIEF single arm protocol Rev C Final 27JAN2021CONFIDENTIAL

anticipated, they will be considered an adverse event and will be recorded on the study Adverse Event CRF.

Symptomatic improvements may not be achieved in all participants receiving the RhinAer procedure and may not be durable beyond the 3-month evaluation in all participants with relief at 3 months.

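### The plan commits to no analysis showing whether response-related dropout has moved the informational 6- to 36-month durability figures

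*Combined protocol and SAP*

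**What the plan says.** The Protocol Summary gives as a secondary objective the evaluation "of treatment effect duration through an extended follow-up to 36 months". Section 6.14 puts its weight on adverse events across the entire "study and the maintenance of the treatment effect over time", and then closes: "Missing data analyses and imputation will not be performed on data collected during the extension phase".

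Two other sections govern the same data:

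- Section 6.6 imputes only for the 3-month primary endpoint, and its optional sensitivity analyses concern the primary analysis. For the rest: "Secondary outcome measures and additional observational measurements will be analyzed by using available data only".
- Section 6.12 allows a model but does not require one: "Repeated measures ANOVA or mixed effects modeling may be used for longitudinal analysis across evaluations".

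The later results have low formal status. Section 3.2 lists them under "Informational outcomes include", and Section 6.12 opens with "Additional outcome measures will be collected for information and hypothesis generating purposes". All three secondary endpoints are at 3 months.

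The plan recognises how bias could arise. Section 4.9.1 warns that improvement "may not be durable beyond the 3-month evaluation in all participants with relief at 3 months", and Section 9.6 names failure to obtain the desired effect as a reason for withdrawal.

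**The concern.** This is a single-arm study, so change from baseline over time is its only evidence on how long benefit lasts. If participants whose response is fading are less likely to complete the later telephone assessments, the available-case means and responder percentages describe those who stayed and are too favourable. If those doing well lose interest instead, the figures are too unfavourable.

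Visit counts (Section 6.8) and recorded withdrawal reasons (Section 9.6) tell a reader how many were lost and, where known, why. They do not tell the reader whether the reported estimates moved. At stake is the reading of the durability results. No confirmatory test depends on them.

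**Working it through.** **Plan's own figures.** The documents state no retention, precision or power figure for the extension. The sample size in Section 6.3 reproduces (paired t-test, 1/3 SD, one-sided 0.025: n = 97, power 0.901), but it concerns the 3-month test and has no bearing here.

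**Inputs from the documents.** Prior-study mean change −5.1 and mean baseline 8.5 (Section 1.0); SD of change 2.6 (Section 6.3, attributed only to a prior study); MCID 1 point (Section 6.2); responder = at least 30% improvement (Section 4.5), taken here as 0.30 × 8.5 = 2.55 points for everyone.

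**Assumptions.** True mean changes of −5.1, −5.0, −4.8, −4.5 and −4.2 at 3, 6, 12, 24 and 36 months; normal scores; correlation 0.6 between visits; every participant has a 3-month score; dropout is permanent; 70% are retained at 36 months; log-odds of dropout change by 0.3 per point of rTNSS change.

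**Truth under these assumptions.** Loss of effect from 3 to 36 months: 5.1 − 4.2 = 0.9 points. Responders at 36 months: Φ((4.2 − 2.55)/2.6) = Φ(0.635), about 74%.

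**Simulated 36-month results (400,000 participants; the last column comes from a re-run of the same model).**

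| Dropout driven by | Available-case mean | Apparent loss from 3 months | Available-case responders | Mixed-model mean | Missing as no change |
|---|---|---|---|---|---|
| Nothing related to response | −4.21 | 0.90 | 73.8% | −4.21 | −2.94 |
| Poor last observed score | −4.59 | 0.52 | 78.9% | −4.21 | −3.20 |
| Good last observed score | −3.83 | 1.28 | 69.4% | −4.21 | −2.68 |
| Poor current, unobserved score | −4.65 | 0.46 | 79.9% | −4.38 | −3.25 |

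**Reading the table.**

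- Poor last score: the available-case error is 4.59 − 4.21 = 0.38 points, and the decline is understated by (0.90 − 0.52)/0.90 = 42%. With good last scores the error is the same size in the other direction.
- The likelihood-based mixed model removes the bias when dropout depends on observed scores. It leaves about 4.38 − 4.21 = 0.17 points when dropout depends on the unobserved current score.
- Missing as no change is roughly 0.70 × the available-case mean. It moves the mean by 4.21 − 2.94 = 1.27 points when dropout is harmless, and is further from the truth than the available-case mean in every row.

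**Range.** Over 54 settings with poor scores driving dropout (retention 85, 70 or 60%; correlation 0.4, 0.6 or 0.8; log-odds 0.15, 0.3 or 0.5 per point; last or current score), the overstatement runs from 0.06 to 1.01 points. A separate two-visit calculation with no true decline (mean improvement 5.1, 15% to 40% missing, correlation 0.5 or 0.7, odds ratio 1.5 or 2.0 per point) gives available-case means of 5.28 to 6.32, an overstatement of about 0.2 to 1.2 points.

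**What a comparison by 3-month response can show.** In the poor-last-score case, 88.5% of those assessed at 36 months were 3-month responders, against 72.5% of those not assessed. With 140 treated, 98 assessed and 42 not, SE = √(0.885 × 0.115/98 + 0.725 × 0.275/42) = 0.076, so the 16-point gap carries a 95% interval of about ±15 points. It is descriptive only.

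**The case against.** The strongest reply has four parts.

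**Section 6.14 need not block the model.** It says extension analyses follow those described earlier, which include the mixed model of Section 6.12. A likelihood model on observed scores imputes nothing and fits the available-data rule. This stands. A reader might infer that the later figures can have no check at all; the documents do not support that. The gap is that the model is optional and unspecified, while Section 6.14 rules out anything labelled a missing-data analysis.

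**The plan works to limit loss.** Later visits are by telephone (Sections 4.1 and 5.6). Everyone is followed to 3 years whatever their response (Section 5.6). Every attempt is to be made to follow those withdrawing for lack of effect, and a participant who misses one visit can return (Section 9.6). Completed questionnaires are reimbursed (Section 9.4). These deserve credit and may keep loss small; the simulation's permanent dropout is harsher than the plan expects. They do not show the effect of whatever loss remains.

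**The stakes are low.** The results are informational, and no success criterion rests on them. This stands, and sets the severity.

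**The magnitude is assumed.** Retention, decline, correlation and dropout strength are not in the documents. The SD is not expressly tied to the study that gave −5.1. The normal model also predicts Φ((5.1 − 3)/2.6), about 79%, improving by at least 3 points, where the prior study reported 88%. The figures show what could happen, not what will.

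**Conclusion.** The concern holds in limited form. Sections 6.14, 6.6 and 6.12 together leave the plan without a committed analysis of whether response-related dropout has moved the 6- to 36-month figures, despite a stated durability objective. This is a written rule, not merely absent detail.

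The central illustration is about 0.4 points, under the assumptions listed. That is below the 1-point MCID, and every available-case and mixed-model mean shown at 36 months still exceeds that MCID. The direction is not known: the bias may be zero or reversed.

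Two stronger readings are not supported. One is that durability will be overstated; that needs retention and dropout patterns the documents do not give. The other is that the primary result is compromised; the 3-month test has its own missing-data rule and does not use extension data. Confidence is high on what the text says and much lower on how much it will matter. Severity: minor.

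**What to change.** 1. **Section 6.12:** replace the permission with a commitment to a likelihood-based mixed model for mean rTNSS change, using all post-baseline visits from 3 to 36 months, reported beside the available-case means.
2. **At each of the four remote visits:** describe assessed and non-assessed participants by their 3-month response.
3. **Section 6.14, last sentence:** reword it so that it no longer bars missing-data analyses, for example by confining it to imputation in the main extension summaries.

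Optionally, report missing as no change (nonresponse) over all treated participants, the Evaluable Population of Section 6.5. Label it only as a conservative lower bound on benefit, since it neither estimates nor corrects the bias. With unrelated dropout and 70% retention it gives about −2.9 against a true −4.2, and 52% responders against 74%. It would need a one-line exception to the available-data rule in Section 6.6.

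The cost is a few lines of plan text, a little more analysis and one extra table per remote visit, all from scores already collected. Limits remain: the model leaves about 0.2 points of bias if unobserved current scores drive dropout, and it addresses mean change, so the responder percentages rely on item 2 and the optional bound.
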